4.1 Primary Efficacy Endpoint

 % detection of RLS/PFO with NB-IS TCD compared against standard of care Transthoracic Echocardiography (TTE)

4.2 Secondary Technical Efficacy Endpoints:

- % agreement for detection of RLS/PFO with NB-IS TCD vs SOC TCD
- % agreement for detection of RLS/PFO with NB-IS TCD vs Transesophageal Echocardiography (TEE)
- % agreement for detection of clinically significant shunts with NB-IS TCD vs TTE
- No window rate (including both unilateral and bilateral absent acoustic windows)
- Success rate of the NB-IS TCD
- Incidence of NB-IS device malfunctions

4.3 Exploratory Endpoints:

 Development of an automated algorithm for Spencer Logarithmic Scale¹⁰ and International Consensus Criteria grading of RLS¹¹

4.4 Primary Safety Endpoint:

Incidence of device-related serious adverse events.

4.5 Secondary Safety Endpoints:

Incidence of procedure-related adverse events related to agitated saline injection before and after VM (headache, allergic reactions, new onset neurological deficit, ischemic stroke, TIA or

DWF-C0001-001 CONFIDENTIAL Page 18 of 44

pulmonary embolism complicating agitated saline contrast injection, etc) will be closely monitored and prospectively collected¹².

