5.1 Study Population Size

To ensure the study is adequately powered, up to 150 subjects will be enrolled at up to 7 centers in the US. The estimation of this sample size has taken into account the prevalence of suboptimal transtemporal windows and potential dropouts.

Once the 150 TTE subjects are enrolled, the study will continue to enroll up to another 150 subjects that received a TTE or TEE until enough TTE subjects have been enrolled in the different grades of the International Consensus Criteria (0,1,2,3) across the TTE Main Study and TTE/TEE Sub Study combined.

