6.14 Study workflow

7 RISKS AND BENEFITS

There is minimal potential clinical risk associated with the scans described in the study. The risks associated with the use of the NeuralBot Investigational System in humans have not been determined as this study is one of the initial uses of the device. An ongoing study utilizing the device in subjects experiencing neurological symptoms of stroke has not reported any unexpected or serious device related adverse events (Protocol No.: NA-01STR-01). The NeuralBot Investigational System is designed to be physically and electro-mechanically safe according to manufacturing standards. At any time, for any reason, the use of the device can be discontinued.

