11.6 Sample Size Calculation

The present study was powered based on the results of a recent meta-analysis reporting a pooled TCD sensitivity of 96.1% for RLS detection, while the pooled TTE sensitivity was estimated at 45.1% (absolute difference of 51%)⁶. For power calculations, we used a more moderate effect size of 40% increase in the sensitivity of NB-IS TCD compared to TTE.

A sample size of 100 subjects achieves 90% power to detect a difference of 40% between two diagnostic tests whose sensitivities are 90% (TCD) and 50% (TTE). This procedure uses a two-sided McNemar test with a significance level of 0.05. The mean prevalence of PFO in the population of patients with cryptogenic stroke is at least 30%². The proportion of discordant pairs has been set at 0.500.

[figure not shown]
		Sensitivity	ity Sensitivity Proportion					
		of Test 1	of Test 2		Discordant	Prevalence		
Power	N	Se1	Se2	Se1-Se2	D	Р	Alpha	Beta
0.00000	10	0.900	0.500	0.400	0.500	0.300	0.05000	
	1.00000							
0.00830	20	0.900	0.500	0.400	0.500	0.300	0.05000	
	0.99170							
0.12990	30	0.900	0.500	0.400	0.500	0.300	0.05000	
	0.87010							
0.32013	40	0.900	0.500	0.400	0.500	0.300	0.05000	
	0.67987							
0.49003	50	0.900	0.500	0.400	0.500	0.300	0.05000	
	0.50997							
0.62345	60	0.900	0.500	0.400	0.500	0.300	0.05000	
	0.37655							
0.72404	70	0.900	0.500	0.400	0.500	0.300	0.05000	
	0.27596							
0.79937	80	0.900	0.500	0.400	0.500	0.300	0.05000	
	0.20063							
0.85654	90	0.900	0.500	0.400	0.500	0.300	0.05000	
	0.14346							
0.89995	100	0.900	0.500	0.400	0.500	0.300	0.05000	
	0.10005							
0.93182	110	0.900	0.500	0.400	0.500	0.300	0.05000	

DWF-C0001-001 CONFIDENTIAL Page 37 of 44

Protocol ID: NA-07BBL-01 Version Date: August 2, 2021

	0.06818						
0.95405	120	0.900	0.500	0.400	0.500	0.300	0.05000
	0.04595						
0.96898	130	0.900	0.500	0.400	0.500	0.300	0.05000
	0.03102						
0.97890	140	0.900	0.500	0.400	0.500	0.300	0.05000
	0.02110						
0.98561	150	0.900	0.500	0.400	0.500	0.300	0.05000
	0.01439						

 $\label{eq:vsN} vs~N$ Se1=0.900 Se2=0.500 D=0.500 α =0.050 P=0.300 2-Sided McNemars Test

Given previous reports indicating a prevalence of suboptimal transtemporal windows in 5% of Hispanic²⁰, 5% of Caucasian²¹, 9% in African American¹⁹ and 14% of Asian²² individuals aged <60 years, we increased our projected sample size by 20% (n=120). In addition, the final sample size

DWF-C0001-001 CONFIDENTIAL Page 38 of 44

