was further increased by 20% (n=144) in order to account for an anticipated dropout rate of 20%. Consequently, the final study sample was set at 144 individuals.

The sensitivity of TCD against TEE for right-to-left shunt detection has been estimated 90% in a recent meta-analysis²⁴. A sample size of 147 patients produces a two-sided 95%CI with a 95%CI width equal to 20% when the sample sensitivity is 90% and the prevalence is 30%. After the first 150 TTE subjects in the Main study are enrolled, the study will continue to enroll up to an additional 150 subjects that received a TTE or TEE bubble study.

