11.7 Primary Safety Endpoint Analysis

Throughout the study we will collect the incidence of device-related adverse events, which will be used to determine the safety of the device within the acute stroke environment. In our EXPEDITE study which is also run in the ER for stroke assessment, the device has been designated minimal risk by the IRB and we have not had any serious adverse events in over 80 subjects. We will continue to closely monitor this metric.

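### Section 11.7 bases the primary safety conclusion on a raw incidence with no interval or bound, and the event type and denominator of that incidence are not settled.

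*Combined protocol and SAP*

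**What the plan says.** Section 4.4 and the synopsis define the primary safety endpoint as "Incidence of device-related serious adverse events". Section 11.7, which is the whole analysis of that endpoint, speaks instead of the "incidence of device-related adverse events, which will be used to determine the safety of the device within the acute stroke environment". It then cites a separate emergency-room study of stroke assessment, in which "we have not had any serious adverse events in over 80 subjects", and says that the metric will be monitored closely. No interval, upper limit, acceptable rate or decision rule for safety appears in 11.7, 4.4, Section 8 or the synopsis.

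The study is labelled pivotal, and Section 4 makes safety part of the objective. Section 7 calls the clinical risk of the scans minimal. It also states that "The risks associated with the use of the NeuralBot Investigational System in humans have not been determined", because this is among the first uses of the device.

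On numbers, 5.1 says that "up to 150 subjects will be enrolled at up to 7 centers in the US". In 11.6 "the final study sample was set at 144 individuals", and after the main study "the study will continue to enroll up to an additional 150 subjects that received a TTE or TEE bubble study". On who counts for safety, 8.2 in one paragraph has subjects with adequate-quality NB-IS data assessed for device-related events, and in the next paragraph all subjects scanned. Section 6.3 removes all clinical and imaging data from the final analysis when the scan quality is inadequate.

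**The concern.** A rate estimated from few or no events means little without its upper limit: an observed 0% excludes quite different levels of harm at 80, 150 and 300 subjects. Section 11.7 uses the incidence to reach a conclusion about safety but plans nothing that tells the reader how much harm has been excluded. The prior result is offered as reassurance in the same way, without its limit.

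The incidence is also not fully defined. Serious device-related events and all device-related events are different numerators. The anticipated events in 7.1 are discomfort and claustrophobia, so the wider count may well not be zero. The denominator could be everyone scanned or only those with a usable recording. An event that interrupts a scan would tend to leave an incomplete recording, and 6.3 would then take that subject's clinical data out of the final analysis. That exclusion can bias the safety result in the device's favour.

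**Working it through.** **The plan's own figures.** No figure is stated for safety, and the main study was sized on sensitivity alone. Section 11.6 says: "A sample size of 100 subjects achieves 90% power to detect a difference of 40% between two diagnostic tests". With 30% prevalence, 100 subjects give 30 with a shunt. A discordant proportion of 0.500 and a difference of 0.400 give cell probabilities of (0.500 + 0.400)/2 = 0.45 and (0.500 − 0.400)/2 = 0.05. An exact two-sided McNemar test at 0.05 then has power 0.89995, as tabulated in 11.6. The two 20% increases give 100 × 1.2 × 1.2 = 144, also as stated. Safety precision plays no part in this.

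**Inputs for the safety check.**
- Prior study: 0 serious events, n = 80 (the text says over 80, so the limit below is slightly too high).
- This study: n = 144 (11.6), 150 (the main-study cap in 5.1), and 300 = 150 + 150 (both caps reached and pooled).
- True serious-event rate p: not in the documents. I assume 1% and show 0.5% to 2%.

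**Formulas.** With zero events in n subjects, the exact (Clopper-Pearson) two-sided 95% upper limit is 1 − 0.025^(1/n). It needs no assumed rate. The chance of seeing no event at a true rate p is (1 − p)^n.

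| n | Upper limit with 0 events | P(0) at 0.5% | P(0) at 1% | P(0) at 2% |
|---|---|---|---|---|
| 80 (prior study) | 4.51% | 67.0% | 44.8% | 19.9% |
| 144 | 2.53% | 48.6% | 23.5% | 5.5% |
| 150 | 2.43% | 47.1% | 22.1% | 4.8% |
| 300 | 1.22% | 22.2% | 4.9% | 0.2% |

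For example, at n = 150 the limit is 1 − 0.025^(1/150) = 0.0243, and 0.99^150 = 0.221. The 100 and 120 in 11.6 are steps before the final inflation, not enrolment targets, so I do not use them as study sizes.

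To exclude 1% with zero events at the two-sided 95% level, n must be at least ln(0.025)/ln(0.99) = 367.04, that is 368. This is more than the maximum of 300. With a one-sided 95% limit the figure is ln(0.05)/ln(0.99) = 298.07, that is 299.

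**The text set side by side.**
- Numerator: 4.4 counts device-related serious events; 11.7 counts device-related events of any severity, yet cites serious events in support.
- Assessed population: 8.2 gives both all scanned subjects and those with adequate-quality data.
- Analysed population: 6.3 excludes the clinical data of inadequate scans and makes no exception for safety.

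**The case against.** The strongest reply is that little turns on this. The device is non-invasive, is modified from a cleared product and is classed as non-significant risk. Section 7 reports no unexpected or serious device-related events in an ongoing study. Single serious events go to the sponsor within 72 hours under 8.4, whatever 11.7 says. A reader given the count and the denominator can compute the interval. All of that stands, and it is why this is a low-cost improvement to the analysis and not a threat to the conduct of the trial. But the reader must first know the denominator, and here the plan conflicts with itself.

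Three stronger readings are tempting, and the documents do not support them.
- A reader might infer that the plan treats a zero count as proof of safety. No such rule is written. Section 11.7 only omits an inferential method and cites a zero count as reassurance.
- A reader might infer that the study would often miss a 1% serious-event rate. The 1% is an assumption. The chance of seeing none is 22% to 24% at 144 to 150 subjects, so it is not the usual result. Events are collected throughout the study, and if 300 are reached and pooled the chance is 5%. Because both parts are capped and not guaranteed, 300 cannot be assumed either.
- A reader might infer that zero or one serious event is to be expected because the study was sized for sensitivity. That depends on the event rate: at 2% and 150 subjects, 150 × 0.02 = 3 events are expected.

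**Conclusion.** The concern holds as a gap in the planned analysis. Section 11.7 draws a safety conclusion from a bare incidence, and the evidence it cites still allows a serious-event rate of about 4.5%. A zero count in this study would still allow about 2.5% at 144, 2.4% at 150 and 1.2% at 300. These limits rest only on the number of subjects and the exact binomial method. The probabilities of seeing no event rest in addition on the assumed rate, and are illustrations. All these figures are for serious events, as in 4.4, and not for the wider count in 11.7.

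The mismatch between 4.4 and 11.7, the two populations in 8.2 and the exclusion in 6.3 must be reconciled, since they decide what the incidence is. The documents do not support saying that the device is unsafe, or that the plan equates zero events with safety.

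**What to change.** In 11.7:
- Report device-related serious adverse events, as defined in 4.4, and separately all device-related adverse events. Give each as a count over all subjects in whom NB-IS use was started, whatever the scan quality, with an exact (Clopper-Pearson) two-sided 95% interval.
- Word the safety conclusion by the upper limit, that is, the serious-event rate above which the data exclude harm at the stated confidence. Otherwise call the analysis descriptive and drop the claim that the incidence determines safety. An interval alone is not a pass/fail rule; if the sponsor wants one, it must also state and justify an acceptable rate.
- State the limits that the design can give with zero events: about 2.5% at 144, 2.4% at 150 and 1.2% at 300.
- Give the prior zero-event result with its upper limit (about 4.5% for 80 subjects), or remove it.

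In 6.3, exempt safety data from the exclusion of inadequate scans. In 8.2, keep a single assessed population: all subjects in whom NB-IS use was started.

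The cost is a few lines of text and the added interval in the safety table, with no extra subjects or procedures. The downside for the sponsor is a less favourable statement: a zero count among 150 subjects would read as rates above about 2.4% excluded, and not simply as 0%.

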11.8 Secondary Safety Endpoint Analysis

Throughout the study we will collect the incidence of procedure-related adverse events related to agitated saline injection before and after VM (headache, allergic reactions, new onset neurological deficit, ischemic stroke, TIA or pulmonary embolism complicating agitated saline contrast injection, etc.) will be closely monitored and prospectively collected¹⁸.

12 ETHICAL CONSIDERATIONS

12.1 Investigational Review Board (IRB) Approval

This study will be conducted using an FDA cleared product called the Lucid M1 System, 510k K160442. The study will also utilize an investigational device, called the NeuralBot Investigational System (NB-IS) 510k K180455 with modifications to facilitate workflow improvements in the study. The modifications do not introduce additional risks and do not alter existing risks and mitigations. All modifications will be tested per NovaSignal's design controls procedures.

This protocol and the informed consent must be reviewed and approved by the appropriate IRB where the study is to be conducted before enrolment of subjects. The NovaSignal and the IRB must approve in writing any changes to the protocol that affect the rights, safety, and/or welfare of the subjects, or may adversely affect the validity of the study.

It is the responsibility of the investigator to submit the final version of the protocol with the Informed Consent Form (ICF), if required, to an appropriately constituted IRB prior to commencement of the study. The Investigator will submit the appropriate documentation if any extension, renewal or amendment of the IRB approval must be obtained. In particular, study plan amendments, ICF changes or other written information provided to the subject must be approved by the IRB in writing, when required.

12.2 Role of NovaSignal

As the study Sponsor of this clinical study, NovaSignal has the overall responsibility for the conduct of the study, including assurance that the study meets the regulatory requirements of the Food and Drug Administration. NovaSignal will ensure adherence to the regulations as outlined in

DWF-C0001-001 CONFIDENTIAL Page 39 of 44

the Sponsor general duties, selection of investigators, monitoring, maintaining records, and submitting reports.

12.3 Investigator Responsibilities

The Principal Investigator (PI) shall be responsible for the day-to-day conduct of the study as well as for the safety and well-being of the human subjects involved in the study. The PI also assumes overall responsibility and accountability for the study team and for data obtained from each subject participating in the study.

The PI shall be responsible for:

- 1. Obtaining a written IRB approval for the study and subject ICF prior to including any subject in this study, as required by local rules and laws.
- 2. Ensuring that the study is conducted in compliance with IRB requirements including conditions which may be imposed by a reviewing IRB.
- 3. Ensuring compliance with the study plan, applicable laws, and applicable regulations.
- 4. Obtaining informed consent and privacy authorization for all study subjects prior to subject participation (the informed consent and privacy authorization processes may be combined, as per usual procedure of the IRB).
- 5. Collecting all required study data on the Case Report Forms provided.
- 6. Reviewing and signing CRF pages indicating documents are accurate and complete.

The PI will agree to provide access to the records of all subjects entered into this study, as well as all other study documentation. In addition, all records may be subject to inspection by officials of US FDA and other regulatory authorities according to local rules and laws.

The PI should make accurate and adequate progress reports to the IRB at appropriate intervals, according to the IRB requirements, when applicable. The PI will inform the IRB of study completion or termination within the time period specified by the IRB, when applicable.

The PI is responsible for informing the IRB of any safety issues related to the study as required.

The PI/site must maintain adequate records on all aspects of the study.

The Pl/site must maintain the study records for at least two years after cessation of the study.

Sub-Investigators will be responsible for study activities in coordination with the PI and in accordance to the study plan. A Sub-Investigator may assume the responsibility of the PI should the PI resign from the study.

12.4 Records Custody

An investigator may withdraw from the study. If the PI withdraws from the study, the responsibility of conducting follow-up and maintaining records must be transferred to another responsible party within institution (i.e. Sub-I). Notice of transfer must be provided in writing by the PI to NovaSignal and the IRB when applicable, not later than 10 working days after transfer occurs.

DWF-C0001-001 CONFIDENTIAL Page 40 of 44

13 APPENDIX

13.1 Spencer Logarithmic Scale (SLS)¹⁰

SLS GRADE	SLS Microembolic Signal (MES) Count
Grade 0	No MES
Grade 1	1 – 10 MES
Grade 2	11 – 30 MES
Grade 3	31 – 100 MES
Grade 4	101 – 300 MES
Grade 5	> 300 MES

13.2 International Consensus Criteria (ICC)¹¹

ICC GRADE	ICC Microembolic Signal (MES) Count
Grade 0	No MES
Grade 1	1 – 20 MES
Grade 2	> 20 MES or "shower" appearance
Grade 3	"curtain" appearance of MES

13.3 Classification of Potential Causative Mechanism in PFO-Associated Stroke¹

		RoPE Score	
Risk Source	Features	Low	High
Very High	A PFO and a straddling thrombus	Definite	Definite
High	(1) Concomitant pulmonary embolism or deep venous thrombosis preceding an index infarct combined with either (2a) a PFO and an atrial septal aneurysm or (2b) a large-shunt PFO	Probable	Highly probable
Medium	Either (1) a PFO and an atrial septal aneurysm or (2) a large-shunt PFO	Possible	Probable
Low	A small-shunt PFO without and atrial septal aneurysm	Unlikely	Possible

